6.3.2 Statistical Hypothesis, model and analysis

Single-stage phase II trials are frequently undertaken to determine whether a new procedure or treatment is likely to meet a basic level of efficacy before comparing it with the standard technique in a larger randomized phase III trial. This study is of a single stage design, which is defined as follows. Let p_0 be the highest proportion of patients progression-free at Month 9 which would indicate that the procedure or treatment is clearly ineffective, and p_1 be the minimum required proportion of patients progression-free to show that the procedure or treatment is effective. The trial tests the null hypothesis H_0 that the proportion of patients progression-free, p , is less than or equal to p_0 against the alternative hypothesis H_1 that p is greater than or equal to p_1 . It consists of entering a predetermined number of patients and

deciding in favor of p_0 or p_1 based on the success rate observed by using an appropriate cut-off between p_0 or p_1 . In a single-stage design, if the number of responses is greater than or equal to $R+1$, the hypothesis that p is less than or equal to p_0 is rejected. If the number of responses is less than or equal to R , the hypothesis that p is greater than or equal to p_1 is rejected.

In this trial, p_0 and p_1 have been set equal to 0.20 and 0.45, respectively. Forty (40) patients are planned to be randomized in each treatment group. If the number of responses is 13 or more, the hypothesis that $p \leq p_0 = 20\%$ is rejected with a target alpha error rate of 5% and an actual alpha error rate of 4.3%; if the number of responses is 12 or less, the hypothesis that $p \geq p_1 = 45\%$ is rejected with an actual beta error rate of 4%.

In the case where more than 40 patients are randomized to one arm, the required number of responses to reject the null and alternative hypotheses will be computed using the methodology described in Fleming's paper [Fleming 1982]. R Codes below compute the cutoff (RstarPlus1) to reject the null hypothesis for different sample sizes.

For example, with 41 patients, the required number of responses to reject the null hypothesis is still 13 responses, and with 42 patients the required number is 14 responses.

```
fleming <- function(n){
p.0 <- 0.2
Z <- qnorm(0.95)
N <- n
s <- round(N * p.0 + Z * sqrt((N * p.0 * (1 - p.0)))) + 1
thres <- list(N = N , RstarPlus1 = s)
return(thres)
}

n <- 40:45
f <- sapply(n, fleming)
f

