Study treatment discontinuation	Point/time when patient permanently stops taking study treatment for any reason; may or may not also be the point/time of premature patient withdrawal
Variable	Identifier used in the data analysis; derived directly or indirectly from data collected using specified assessments at specified timepoints

Amendment 5

Amendment rationale

In total, 124 patients have been randomized in the trial. 43 patient completed the core phase of the study and 41 entered in the extension phase. So far, 30 patients have discontinued the study treatment and 11 patients are still ongoing in the Extension phase.

The primary analysis of the study data was performed on 26th February 2016. For the core phase analysis, the data cutoff that was applied for a patient was either 12 months of study treatment or “End of Core Phase Evaluation” phase.

The primary efficacy endpoint was defined as the proportion of patients who were progression free at Month 9, based on RECIST V1.1. The primary analysis was to check if a sufficient number of patients were progression free at month 9 and the null hypothesis would be either accepted or rejected on the basis of the total number of responders. Accordingly, it would be concluded that the primary objective has been met/not met.

While performing the primary analysis for PFR at month 9, it was observed that enough number of responses was observed in all the treatment arms. In case of Pasireotide-LAR and combination arm, 13 patients had responses out of 41 patients and for Everolimus, 14 patients had responses out of 42 patients. The observed number of responses was enough to claim that the null hypothesis can be rejected. Hence it can be said that the primary objective was met.

The Study Steering Committee assessed the results of the primary endpoint during the Steering Committee Meeting held in May 2016. As patients were receiving a benefit from participation in the study, the study protocol is being amended. This amendment includes details to extend the duration of the study [from 104 weeks (2 years) to as long as all patients continue to demonstrate benefit and do not fulfill any of the study discontinuation criteria]. Only tumor evaluation and safety data will be collected after the 4th Visit in the Extension Phase. In addition to that, some sections of the protocol have been clarified and some inconsistencies corrected.” **Other major changes implemented with the current protocol are:**

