10.8 Sample size calculation

A Fleming single stage design will be employed for each arm. Let p_0 be the highest proportion of patients progression-free at Month 9 which would indicate that the treatment is clearly ineffective, and p_1 be the minimum required proportion of patients progression-free. The trial tests the null hypothesis H_0 that the observed proportion of patients progression-free, p , is less than or equal to p_0 against the alternative hypothesis H_1 that p is greater than or equal to p_1 . It consists of entering a predetermined number of subjects and deciding in favor of p_0 or p_1 based on the success rate observed by using an appropriate cut-off between p_0 and p_1 . If the number of responses is greater than or equal to $R+1$, p_0 is rejected. If the number of responses is less than or equal to R , p_1 is rejected.

In this trial, p_0 and p_1 have been set equal to 0.20 and 0.45, respectively. Forty (40) patients are planned to be randomized in each treatment group. If the number of responses is 13 or more, the hypothesis that $p \leq p_0 = 20\%$ is rejected with a target alpha error rate of 5% and an actual alpha error rate of 4.3%; if the number of responses is 12 or less, the hypothesis that $p \geq p_1 = 45\%$ is rejected with an actual beta error rate of 4%.

Table 10-2 Design features for single-arm trials

p0	p1	Target		Cut-Off R + 1	N	Actual	
		alpha	beta			alpha	beta
20%	45%	5%	10%	13	40	4.3%	4%

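### At 41 patients the SAP's cut-off of 13 responses has an exact one-sided alpha of 5.2%, above the 5% target and not reported, and two arms were declared positive at exactly 13/41

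*SAP*

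**What the plan says.** Each arm is tested separately against p0 = 0.20, with p1 = 0.45, a target alpha of 5% and a target beta of 10%. For 40 patients the cut-off is 13 responses. Protocol section 10.8 says that the null hypothesis "is rejected with a target alpha error rate of 5% and an actual alpha error rate of 4.3" percent, with an actual beta of 4%. SAP sections 6.3.2 and 13 repeat these figures.

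SAP section 6.3.2 then covers larger arms: "In the case where more than 40 patients are randomized to one arm", the cut-off is recomputed by Fleming's method with the R line "s <- round(N * p.0 + Z * sqrt((N * p.0 * (1 - p.0)))) + 1". The printed cut-offs for n = 40 to 45 are 13, 13, 14, 14, 14, 14, and the text confirms that "with 41 patients, the required number of responses to reject the null hypothesis is still 13 responses". No actual alpha or beta is given for any n above 40.

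The Amendment 5 rationale in the protocol reports the outcome: "In case of Pasireotide-LAR and combination arm, 13 patients had responses out of 41 patients", and 14 of 42 responded on everolimus. It concludes: "The observed number of responses was enough to claim that the null hypothesis can be rejected".

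**The concern.** The code rounds a normal approximation to the nearest integer and never checks the binomial tail that results. Rounding down can leave the cut-off one response too low for the stated target. At n = 41 it does so, and 41 is the size reported for two of the three arms, both of which landed exactly on the cut-off.

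SAP section 13 treats a rejection as grounds for moving to phase III, and SAP sections 6.3.2 and 6.3.3 pass the arms that reject on to the choice of a best arm. Someone who reads only the 5% target and the 4.3% actual alpha would take the latter to describe the reported result. It belongs to a sample size that none of the three reported denominators has.

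A related gap is which n the rule uses. It is triggered by the number randomized, but the result is presented for the full analysis set. That set requires at least one dose (SAP section 3.6) and can lose patients with severity code 0 deviations (SAP section 3.5).

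**Working it through.** **Inputs.** p0 = 0.20, p1 = 0.45, one-sided 5% with Z = 1.645, and the cut-off formula (SAP 6.3.2). Counts of 13/41, 13/41 and 14/42 (Amendment 5 rationale). The same rationale says "In total, 124 patients have been randomized in the trial", and 41 + 41 + 42 = 124.

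**Step 1: reproduce the printed figures.** For n = 40 and cut-off 13, the exact binomial gives

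- alpha = P(X ≥ 13 | 40, 0.20) = 4.32%
- beta = P(X ≤ 12 | 40, 0.45) = 3.86%

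These match the printed 4.3% and 4%. The normal approximation at n = 40 would give an alpha of 2.4%, or 3.8% with continuity correction. The SAP's actual alpha is therefore an exact binomial quantity, and the like-for-like figure at other sizes must be exact too.

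**Step 2: reproduce the extended cut-offs.** The formula is n·p0 + Z·√(n·p0·(1 − p0)), rounded, plus 1.

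- n = 41: 8.2 + 1.645 × √6.56 = 12.413, rounded to 12, plus 1 = 13
- n = 42: 8.4 + 1.645 × √6.72 = 12.664, rounded to 13, plus 1 = 14

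The whole printed row reproduces.

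**Step 3: exact error rates of the SAP rule.** The last column is the smallest r with P(X ≥ r | n, 0.20) ≤ 0.05.

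| n | Formula before rounding | SAP cut-off | Exact alpha | Exact beta | Exact 5% cut-off |
|---|---|---|---|---|---|
| 40 | 12.161 | 13 | 4.32% | 3.86% | 13 |
| 41 | 12.413 | 13 | **5.21%** | 2.93% | 14 |
| 42 | 12.664 | 14 | 2.98% | 4.54% | 14 |
| 43 | 12.914 | 14 | 3.62% | 3.49% | 14 |
| 44 | 13.164 | 14 | 4.37% | 2.66% | 14 |
| 45 | 13.414 | 14 | **5.21%** | 2.01% | 15 |

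A cut-off of 14 at n = 41 has alpha 2.42% and beta 5.86%, inside both the 5% and the 10% targets. A cut-off of 15 at n = 45 has alpha 2.50% and beta 4.09%.

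**Step 4: apply to the reported counts.**

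| Arm | Count | Exact one-sided p | 90% exact interval | Lower limit of 95% exact interval |
|---|---|---|---|---|
| Pasireotide LAR | 13/41 | 0.052 | 19.9% to 45.6% | 18.1% |
| Combination | 13/41 | 0.052 | 19.9% to 45.6% | 18.1% |
| Everolimus | 14/42 | 0.030 | 21.4% to 47.1% | 19.6% |

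**Step 5: sensitivity to the denominator.** With 13 responses, alpha is 3.55% at n = 39, 4.32% at n = 40 and 5.21% at n = 41. With 14 responses, it is 1.94% at n = 40, 2.42% at n = 41 and 2.98% at n = 42.

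**The case against.** The SAP followed its own rule. The code gives what the SAP prints, the 4.3% is explicitly tied to 40 patients, and nothing in the SAP claims it for 41. The method is a published large-sample one; with continuity correction the approximation gives 4.7% at n = 41. The binomial is discrete: the two levels available there are 5.21% and 2.42%, and the SAP's choice is the nearer to 5%. It can also be said that the borderline status would show anyway, because SAP 6.3.2 plans an exact interval and SAP 6.3.3 plans the posterior probability that the rate is at most 20% (about 4.1% for 13/41 and 2.3% for 14/42). The final choice among arms rests on risk and benefit, and no document shows it turning on 5.2% against 5.0%.

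Much of this stands. The rule was met, and the excess is 0.2 points. It does not remove the problem. The SAP's own standard at n = 40 is an exact alpha below target, and at n = 41 a cut-off that meets both targets existed. The planned outputs do not reveal the excess. SAP 6.3.2 states no level for the exact interval, and a 95% interval falls below 20% in all three arms, so it cannot show which of them reject at one-sided 5%. The posterior probability is not an error rate.

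**Conclusion.** The point holds. At n = 41 the SAP's cut-off of 13 has an exact one-sided alpha of 5.21% against a 5% target, and neither document reports it. By the SAP's rule all three arms reject. At an exact 5% level only everolimus does.

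The conclusion for the other two arms assumes that 41 is their full analysis set size. The arm totals add to the 124 randomized, but the documents do not show that all of them were dosed. One undosed or excluded non-responder would bring an arm to 13/40 and 4.3%. Everolimus stays below 5% at n = 40, 41 or 42. The n = 45 row has the same excess but affects no reported result.

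**What to change.** 1. Tabulate the exact alpha and beta of the SAP rule at the n analysed in each arm, and state whether that n is patients randomized or the full analysis set.
2. State that the pre-specified rule was met at 13/41, with an actual alpha of 5.2% (p = 0.052) if the full analysis set is 41, rather than 4.3%, and that this lies outside the 5% target.
3. Show the 90% exact interval beside each count, because it corresponds to a one-sided 5% test.
4. Give the exact cut-offs (13 at n = 40, 14 at n = 41 to 44, 15 at n = 45) as a sensitivity decision only. The pre-specified rule should not be replaced, because the counts are already known: "The primary analysis of the study data was performed on 26th February 2016".

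The cost is one small table and a few sentences in the SAP and study report. It needs no patients and no new data, and the pre-specified decision is unchanged. The evidence for two arms will be visibly borderline.

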##           [,1] [,2] [,3] [,4] [,5] [,6]
## N          40  41  42  43  44  45
## RstarPlus1 13  13  14  14  14  14
```

Each arm will be independently evaluated using the above decision rule.

If the null hypothesis is rejected for more than 1 arm the selection of the best arm will be based on a risk/benefit evaluation and guided by a Bayesian evaluation described below.

The number and percentage of patients progression-free at Month 9 (PFR-9) will be presented for the FAS together with their confidence interval. An *exact binomial confidence interval* (implemented using SAS procedure FREQ with EXACT statement for one-way tables) will be calculated [Clopper & Pearson, 1934].

The same computations will be repeated for each stratification factor by stratum.

6.3.3 Supportive analyses

To further support the decision process, a Bayesian analysis will be performed to estimate the proportion of patients who are progression-free at Month 9 for each treatment arm.

Vague prior beliefs about the PFR-9 distribution reflecting the current uncertainty about the efficacy of Everolimus and Pasireotide alone or in combination in the study will be summarized in prior distributions. Minimally informative Beta distribution priors ([Neuenschwander, Branson and Gsponer 2008]) with prior median equal to the clinical threshold for futility (20%) will be utilized.

The parameter values of the prior distribution for PFR-9 by arm are summarized in table 5 and table 6 summarizes the corresponding prior distribution that PFR-9 falls within the pre-specified efficacy intervals

Table 5 - Prior parameters for minimally informative Beta distribution of PFR at 9 months

Prior parameters	
α	β
0.431	1

Table 6 - Summary of prior distribution of PFR at 9 months

Efficacy intervals			Mean	SD	Quantiles		
Prior probabilities (%) that PFR is in interval:					2.5%	50%	97.5%
Unacceptable	Moderate	Substantial					
[0, 20%]	(20%, 45%]	(45%, 100%]					
0.500	0.209	0.291	0.301	0.294	<0.001	0.2	0.943

The posterior distribution of the PFR-9 is the update of the prior distribution with all the available data from the FAS upon completion of the 9 month follow up. The posterior distribution will be used to derive the probability that the true rate lies in the pre-specified efficacy intervals.

In order to guide the selection of the best treatment for further development, for each treatment arm selected by the Fleming procedure, the probability that the treatment is the best will be evaluated based on the posterior distributions of the PFR-9.

For example, if two treatments A & B are selected using the Fleming single stage method with 13 and 14 successes respectively, the posterior probability of being the ‘best’ treatment is 0.4 and 0.60 respectively for treatment A and treatment B, based on a total of 40 patients per arm and prior distributions of the rate as defined above. The computations are based on Monte Carlo simulations i.e. draws from the posterior Beta distributions of the rates. At each iteration of the simulations, the two treatment rates are compared and the frequency of a treatment coming up better is computed.

If more treatment arms are selected by the Fleming single stage method then 10000 draws will be performed from the posterior Beta distributions to decide on the best treatment arm. A random seed of 43985 will be used.

The number and percentage of patients progression-free will be presented additionally for the PP set, together with the appropriate exact confidence interval (implemented using SAS procedure FREQ with EXACT statement for one-way tables) [Clopper & Pearson, 1934].

Results of supportive analyses will be interpreted purely exploratory.

7 Secondary efficacy evaluations

7.1 Progression-free survival (PFS)

The progression-free survival (PFS) is defined as the time from first study drug administration to objective tumor progression or death from any cause (including extension phase data, if applicable at the time of the extension phase analyses). If a patient has not had an event, PFS is censored at the date of the last adequate tumor assessment. PFS will be analyzed in the FAS and PP set (for both core and extension phases) by presenting the Kaplan-Meier curve and estimators.

The Kaplan-Meier estimate of the PFS survival function will be constructed and displayed by treatment arm overall and per stratum for the core phase analyses and extension phase analyses. The plots will also display the number of patients at risk every 3 months. Median PFS for each treatment arm will be obtained along with 95% confidence intervals calculated by SAS procedure LIFETEST using method of Brookmeyer and Crowley (1982). 25% and 75% percentiles will be calculated as well. K-M event-free probability estimates with 95% confidence intervals using the Greenwood formula will be summarized as well at the following time points: 3, 6, 9, and 12 months. This analysis will be repeated for the FAS set after completion of the extension phase and interpreted exploratory. The progression-free survival analysis after extension phase will take into consideration evaluations during extension phase as well, if a patient has not had an event (discontinued for other reason than PD or death or trial was ended), PFS is censored at the date of the patient's last adequate tumor assessment in study.

Time to progression and death will be listed per patient presenting the start and end date of treatment, the progression status (Y/N), progression date, last progression-free date, death status (Y/N), date of death along with principal cause of death and date of last adequate tumor assessment which is used for censoring.

7.2 Disease Control Rate

The endpoint of disease control rate (DCR) is defined as the proportion of patients showing a best overall response of CR or PR or SD during the core study (12 months) according to RECIST V 1.1. The disease control rate will be calculated for the full analysis set. An *exact binomial confidence interval* (implemented using SAS procedure FREQ with EXACT statement for one-way tables) will be calculated [Clopper & Pearson, 1934].

7.3 Time to Response

Time to response is defined as the time from start of treatment to the first objective tumor response (PR or CR) observed up to 12 months (i.e. core phase) according to RECIST V. 1.1 criteria. Patients who did not achieve a confirmed PR or CR will be censored using one of the following options:

- At maximum follow-up (i.e. FPFV to LPLV used for the analysis) for patients who had a PFS event (i.e. progressed or died due to any cause). In this case, the PFS event is the worst possible outcome as it means the patient cannot subsequently respond.
- At last adequate tumor assessment date otherwise. In this case patients have not yet progressed so they theoretically still have a chance of responding.

Time to response will be explored by presenting the Kaplan-Meier curve and estimators along with associated 95 percent confidence intervals, the number with the event and the number censored for the full analysis set.

7.4 Duration of Response

Duration of response is defined as the time from onset of the first objective tumor response (CR/PR) to objective tumor progression or death from any cause. The start date is the date of first documented response (CR or PR) during core phase and the end date and censoring is defined the same as that for time to progression. The duration of response will be summarized for the subset of patients who had confirmed response. Duration of response will be explored by presenting the Kaplan-Meier curve graphically and presenting the number of patients with the event, the number censored, the estimators and associated 95 percent confidence intervals. The results from this analysis should be interpreted with caution since treatment bias could be introduced, as only those patients with a response will be included and the number may vary between treatments.

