10.5.2 Other secondary efficacy objectives

[figure not shown]
Progression-free survival (PFS) is defined as the time from first study drug administration to objective tumor progression or death from any cause. If a patient has not had an event, PFS is censored at the date of the last adequate tumor assessment. PFS will be analysed in the FAS and PP set by presenting the Kaplan-Meier curve and estimators.

Disease control rate (i.e. the proportion of patient showing a best overall response of CR, PR or SD) at 12 months. It will be calculated and displayed with 95 percent exact confidence intervals.

Time to response will be defined as the time from start of treatment to the first objective tumor response (PR or CR) observed according to RECIST V. 1.1 criteria. Patients who did not achieve a confirmed PR or CR will be censored using one of the following options:

- at maximum follow-up (i.e. FPFV to LPLV used for the analysis) for patients who had a PFS event (i.e. progressed or died due to any cause). In this case, the PFS event is the worst possible outcome as it means the patient cannot subsequently respond;
- at last adequate tumor assessment date otherwise. In this case patients have not yet progressed so they theoretically still have a chance of responding.

Time to response will be explored by presenting the Kaplan-Meier curve and estimators.

Duration of response is defined as the time from onset of the first objective tumor response (CR/PR) to objective tumor progression or death from any cause. Patients not experiencing progression or death will be censored with the date of their last adequate tumor assessment. Duration of response will be explored by presenting the Kaplan-Meier curve and estimators.

Objective response rate is defined as the proportion of patients showing a best overall response of CR or PR at 9 and 12 months, according to RECIST V. 1.1 criteria. The objective response rate will be calculated and displayed with 95 percent exact confidence intervals for the full analysis set.

Best overall response is defined as the best response recorded from the start of the treatment until disease progression/recurrence, taking as reference for PD the smallest measurements recorded since the treatment started.

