14.1.3.2.3 Time to progression

Some studies might consider only death related to underlying cancer as an event which indicates progression. In this case the variable “Time to progression” might be used. TTP is defined as PFS except for death unrelated to underlying cancer.

Time to progression (TTP) is the time from date of randomization/start of treatment to the date of event defined as the first documented progression or death due to underlying cancer. If a patient has not had an event, time to progression is censored at the date of last adequate tumor assessment.

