14.1.3.2.9 Sensitivity analyses

This section outlines the possible event and censoring dates for progression, as well as addresses the issues of missing tumor assessments during the study. For instance, if one or more assessment visits are missed prior to the progression event, to what date should the progression event be assigned? And should progression event be ignored if it occurred after a long period of a patient being lost to follow-up? It is important that the protocol and RAP specify the primary analysis in detail with respect to the definition of event and censoring dates and also include a description of one or more sensitivity analyses to be performed.

Based on definitions outlined in [Section 14.1.3.2.7](#), and using the draft FDA guideline on endpoints (Clinical Trial Endpoints for the Approval of Cancer Drugs and Biologics, April 2005) as a reference, the following analyses can be considered:

Table 14-5 Options for event dates used in PFS, TTP, duration of response

[figure not shown]
Situation		Options for end-date (progression or censoring) ¹ (1) = default unless specified differently in the protocol or RAP	Outcome
A	No baseline assessment	(1) Date of randomization/start of treatment ³	Censored
B	Progression at or before next scheduled assessment	(1) Date of progression (2) Date of next scheduled assessment ²	Progressed Progressed
C1	Progression or death after exactly one missing assessment	(1) Date of progression (or death) (2) Date of next scheduled assessment ²	Progressed Progressed
C2	Progression or death after two or more missing assessments	(1) Date of last adequate assessment ² (2) Date of next scheduled assessment ² (3) Date of progression (or death)	Censored Progressed Progressed
D	No progression	(1) Date of last adequate assessment	Censored
E	Treatment discontinuation due to 'Disease progression' without documented progression, i.e. clinical progression based on investigator claim	(1) N/A (2) Date of discontinuation (visit date at which clinical progression was determined)	Ignored Progressed
F	New anticancer therapy given	(1) Date of last adequate assessment (2) Date of secondary anti-cancer therapy (3) Date of secondary anti-cancer therapy (4) N/A	Censored Censored Event Ignored
G	Deaths due to reason other than deterioration of 'Study indication'	(1) Date of last adequate assessment	Censored (only TTP and duration of response)

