14.1.4.5.6 Censoring reason

In order to summarize the various reasons for censoring, the following categories will be calculated for each time to event variable based on the treatment completion page, the study evaluation completion page and the survival page.

For survival the following censoring reasons are possible:

- Alive
- Lost to follow-up

For PFS and TTP (and therefore duration of responses) the following censoring reasons are possible:

- Ongoing without event
- Lost to follow-up
- Withdrew consent
- Adequate assessment no longer available*
- Event documented after two or more missing tumor assessments (optional, see Table 3-2)
- Death due to reason other than underlying cancer (*only used for TTP and duration of response*)
- Initiation of new anti-cancer therapy

*Adequate assessment is defined in [Section 14.1.3.2.7](#). This reason is applicable when adequate evaluations are missing for a specified period prior to data cut-off (or prior to any other censoring reason) corresponding to the unavailability of two or more planned tumor assessments prior to the cut-off date. The following clarifications concerning this reason should also be noted:

- This may be when there has been a definite decision to stop evaluation (e.g. reason="Sponsor decision" on study evaluation completion page), when patients are not followed for progression after treatment completion or when only UNK assessments are available just prior to data cut-off).
- The reason "Adequate assessment no longer available" also prevails in situations when another censoring reason (e.g. withdrawal of consent, loss to follow-up or alternative anti-

cancer therapy) has occurred more than the specified period following the last adequate assessment.

- This reason will also be used to censor in case of no baseline assessment.

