3.2 Secondary objectives

- To assess overall progression-free survival (PFS) throughout the study in patients with a well differentiated neuroendocrine tumor of the lung or thymus. The endpoint “**progression-free survival (PFS)**” is defined as the time from first study drug administration to objective tumor progression or death from any cause, according to RECIST V. 1.1.
- To assess the **disease control rate** of pasireotide LAR and everolimus alone or in combination, at 12 months, in patients with a well differentiated neuroendocrine tumor

of the lung or thymus. Disease control rate is defined as the proportion of patients showing a best overall response of complete (CR) or partial (PR) response or stable disease (SD) according to RECIST V.1.1

- To assess the time to response, duration of response, objective response rate and best overall response of pasireotide LAR and everolimus alone or in combination during 12 months of treatment in patients with a well differentiated neuroendocrine tumor of the lung or thymus. The endpoint **“time to response”** is defined as the time from start of treatment to the first objective tumor response (PR or CR) observed, according to RECIST V.1.1. The endpoint **“duration of response”** is defined as the time from onset of the first objective tumor response (CR/PR) to objective tumor progression or death from any cause. Tumor response will be analyzed using the criteria of confirmation, i.e. patients will need to have confirmed CR or PR overall assessment before PD or end of core phase measured at least 4 weeks apart each other to be included in the subset of responders. The endpoint **“objective response rate”** is defined as the percentage of patients showing a best overall response of CR or PR according to RECIST V.1.1. criteria. Objective response rate will be summarized at 9 months and again at 12 months. The endpoint of **“best overall response”** is defined as the best response recorded from the start of the treatment until disease progression/recurrence, taking as a reference for PD the smallest measurements recorded since the treatment started.

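### SAP 7.4 ends duration of response at any death but borrows the time-to-progression censoring rule, under which non-cancer deaths are censored

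*SAP*

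**What the plan says.** SAP 7.4 gives two instructions in consecutive sentences. The first runs the endpoint from first response "to objective tumor progression or death from any cause". The second says that "the end date and censoring is defined the same as that for time to progression".

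The trial-specific text elsewhere agrees with the first instruction:

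- SAP 3.2 measures the endpoint "from onset of the first objective tumor response (CR/PR) to objective tumor progression or death from any cause".
- Protocol 10.5.2 adds an explicit censoring rule: "Patients not experiencing progression or death will be censored with the date of their last adequate tumor assessment".

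The second instruction depends on a definition that the SAP does not contain. The only one is in protocol Appendix 1, which SAP 6.1 adopts except where the SAP notes otherwise:

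- Appendix 14.1.3.2.3 describes TTP as the time to an "event defined as the first documented progression or death due to underlying cancer", and adds that "TTP is defined as PFS except for death unrelated to underlying cancer".
- Appendix 14.1.3.2.5, on duration of response, contains the same cross-reference to TTP that SAP 7.4 uses.
- Table 14-5, situation G (Appendix 14.1.3.2.9), sends deaths from other causes back to the last adequate assessment, with the outcome "Censored (only TTP and duration of response".
- Appendix 14.1.4.5.6 lists "Death due to reason other than underlying cancer" as a censoring reason and reserves it for TTP and duration of response.

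**The concern.** An endpoint can have only one event definition. Here a responder who dies of, say, an infection with no progression on record ends the response at death under the first sentence of SAP 7.4. Under the second, the same patient is censored at the last scan. A program that follows the second sentence estimates something other than the endpoint named in SAP 3.2, SAP 7.4 and protocol 10.5.2.

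Deaths of this kind are not far-fetched. Protocol 1.2.2.3 reports fatal cases of infection reactivation, renal failure and pneumocystis pneumonia with everolimus. Censoring such a death takes the patient out of the risk set as though later follow-up were merely unobserved, when in fact the response has ended. In expectation that lengthens the Kaplan-Meier duration. At stake is one reported secondary result: its meaning, and possibly its value.

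**Working it through.** The plan states no median, event count or power for duration of response, so there is no figure of its own to reproduce. The check is mainly one of text, followed by an illustration of direction and size.

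**1. One patient under both rules.** Take a confirmed responder with a last adequate scan 3 months after onset of response, no progression, and a non-cancer death at month 4.

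- SAP 7.4 first sentence, SAP 3.2, protocol 10.5.2: event at month 4.
- SAP 7.4 second sentence, read with Appendix 14.1.3.2.3, Table 14-5 situation G and 14.1.4.5.6: censored at month 3.

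For progression, cancer death, or neither progression nor death, the two rules agree. The conflict is confined to this one kind of patient.

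**2. Whether precedence settles it.** Table 14-5 labels its first options as defaults that the protocol or the analysis plan may override, and protocol 10.5.2 does override situation G. But the SAP is also a place where the choice may be made, and its second sentence chooses TTP. The precedence wording therefore does not resolve the conflict.

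**3. Effect on a small sample.** Five hypothetical responders: the patient above, progressions at months 6 and 9, and two still in response at month 9.

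- Any-death rule: 4/5 = 0.80 at month 4; × 3/4 = 0.60 at month 6; × 2/3 = 0.40 at month 9.
- TTP rule: 3/4 = 0.75 at month 6; × 2/3 = 0.50 at month 9.

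**4. Expected size under a model.** Let all events occur at constant hazard λ, with a share f being non-cancer deaths. The any-death median is ln 2/λ. If non-cancer deaths are censored, the hazard is (1 − f)λ and the median is ln 2/((1 − f)λ). The ratio is 1/(1 − f):

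- f = 0: 1.00
- f = 5%: 1.05
- f = 10%: 1.11
- f = 20%: 1.25

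A simulation of 40,000 responders with 3-monthly scans (the interval in protocol 4.1.2) and an assumed true median of 12 months gave these proportions in response at 9 months, any-death against TTP rule: 0.59 and 0.61 at f = 5%, 0.60 and 0.63 at 10%, 0.59 and 0.66 at 20%. The values of f and the median are assumptions; the documents give neither.

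**5. Direction in very small samples.** Two responders: one progresses at month 5, the other dies at month 6 of a non-cancer cause with a last scan at month 4. At month 5 the any-death rule gives 1/2 = 0.50. Under the TTP rule the second patient has already left the risk set at month 4, so the estimate is 0/1 = 0.00. Overstatement is the expected direction, not a certainty.

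**6. Likely numbers.** Response rates quoted from other studies run from 2.0% (protocol 1.2.1.3.1) to 22% (protocol 1.2.2.3.1). Applied to 41 patients, the arm size given in the Amendment 5 rationale for two of the arms, that is 41 × 0.02 = 0.8 to 41 × 0.22 = 9.0, or about 1 to 9 responders per arm. Those populations and regimens differ, so this is only an order of magnitude.

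**The case against.** The best defence is that the any-death definition is the dominant one. It appears in SAP 3.2, in SAP 7.4 itself and in the body of the protocol. Protocol 10.5.2 supplies a full censoring rule, and Appendix 1 is a generic guideline adopted only where nothing else is noted. On that reading the TTP phrase is leftover guideline wording, and a sensible programmer would count every death. The endpoint is also descriptive, restricted to confirmed responders, and SAP 7.4 already advises caution. The Amendment 4 rationale dropped TTP as an endpoint because it expected TTP and PFS results to be equivalent.

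Much of this stands. It limits the consequence and makes the any-death rule the natural choice for repair. It does not remove the conflict, because the sentence that assigns end dates and censoring is the one that points to TTP.

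A reader might also infer that the programmer will have followed that sentence. The programming specifications are not among the documents, so this cannot be known. Nor does the SAP simply depart from a consistent protocol: the protocol disagrees with itself, 10.5.2 against Appendix 1, and SAP 7.4 carries both sides forward.

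**Conclusion.** SAP 7.4 contradicts itself and needs a single stated rule. If a confirmed responder dies of a non-cancer cause without documented progression, TTP censoring turns an event into a censored observation and would tend to overstate duration of response. The size cannot be derived from the documents. The 5% to 25% longer median rests on constant hazards and an assumed non-cancer share of 5% to 20%; with no such deaths the effect is nil.

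A reader might conclude that the reported duration is overstated. The documents do not support that: they report no such death among responders, they do not show which rule was applied, and in a very small sample the difference can go the other way. The Month 9 primary endpoint, the choice between arms and PFS do not depend on this rule. It is a correction that should be made to one secondary analysis, not a threat to the trial's conclusions.

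**What to change.** In SAP 7.4, replace the reference to TTP with a rule written out in full: the event is progression or death of any cause, and patients with neither are censored at their last adequate tumor assessment, using core-phase data. Writing it out is safer than pointing to SAP 7.1, whose PFS definition takes in extension data; under SAP 3.4.2 only PFS and the safety analyses are repeated after the extension.

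Add a statement that Table 14-5 situation G and the non-cancer-death censoring reason in Appendix 14.1.4.5.6 do not apply to duration of response. Otherwise SAP 6.1 leaves the same conflict in force. If a TTP-type version is wanted, label it as a sensitivity analysis.

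Then check which rule the core analysis used. The Amendment 5 rationale dates the primary analysis to 26 February 2016, so this means looking back at an existing result. If TTP censoring was applied, re-derive that table and its curve.

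The cost is a short SAP edit, one censoring flag, possibly a small re-run of one descriptive secondary table, and possibly a shorter reported duration.
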